MLM can accommodate data missing at random, using maximum likelihood-derived estimates based on all available data. That said, data may be missing not at random (MNAR). That is, the outcome data may be systematically missing, for instance, from participants who experience no benefit from CBT-I. Nevertheless, even in the case of MNAR data, estimates derived from analyses examining Hypothesis 2 (addressing the within-person associations of change in insomnia with change in CVD risk) and the Supplemental Aim are unlikely to be affected by data missingness. After all, even if participants who benefit the least from CBT-I drop out of the study, we still anticipate observing the same magnitude of association between improved sleep and changes in cardiovascular biomarkers and QoL. By contrast, Hypothesis 1, which examines clinical response to CBT-I, would be affected by MNAR data. As such, we will conduct sensitivity analysis on three missing data approaches for Aim 1. First, we will conduct a completer analysis, analyzing only data from participants who complete each of the three assessments. Second, we will allow the maximum-likelihood estimation to generate estimates for all available data. In a third approach, we will use an intent-to-treat approach, assuming that missing post-intervention and/or 6-month follow-up data are evidence of stagnation. Specifically, we will use last observation carried forward in the cases of missing data.

D.3. Primary and Secondary Analyses

To examine the degree to which CBT-I is associated with improved sleep efficiency and insomnia severity index score (manipulation check), linear MLM will be used to model sleep outcomes as a function of treatment (CBT-I, control), time (baseline, post-intervention, 6-month follow-up), and the interaction between treatment and time. Planned treatment contrasts in change from baseline to post-intervention and 6-month follow-up will be examined within the context of the model. To determine the degree to which CBT-I is associated with improved CVD risk biomarkers (Hypotheses 1a), each of the 6 CVD risk variables (24-hr SBP, nighttime SBP dipping, FMD, 24-hr epinephrine, and norepinephrine) will also be modeled as a function of treatment, time, and their interaction, with planned treatment contrasts in change from baseline at post-intervention and 6-month follow-up. Dichotomized 10-year ASCVD risk scores (Hypothesis 1b) and QoL scores (Hypothesis 1c) will similarly be modeled via logistic MLM.

To examine whether increased sleep efficiency is associated with decreased CVD risk (Hypothesis 2), lagged values will be used to create changes scores, defined by subtracting values for sleep efficiency and each of the CVD risk parameters measured at time $t-1$ from those measured at time t . Thus, decreases will be reflected by negative change scores and increases by positive change scores. Linear MLM will then be used to model each of the change scores corresponding to the 6 aforementioned CVD risk variables using the general equation below:

$$\text{CVD risk}_{\Delta t} = B0 + B1 * \text{Sleep efficiency}_{\Delta t} + B2 * \text{CVD risk}_{t-1} + B3 * \text{Sleep efficiency}_{t-1}$$

where change in the CVD risk outcome from $t-1$ to t will be modeled as a function of corresponding change in sleep efficiency, covarying for sleep efficiency measured at $t-1$ and the outcome in question measured at $t-1$. To explore the heterogeneity of CBT-I treatment response on sleep (Supplemental Aim), potential moderators (trauma type, insomnia phenotype, medication use, biological sex, and minority status) of the effect of CBT-I treatment on sleep outcomes will be examined via interaction effects. Specifically, sleep efficiency and sleep quality measured at baseline, post-intervention, and 6-month follow-up will be modeled in separate analyses as a function of treatment, time, a given moderator, and their second- and third-order interactions. To avoid the effects of multicollinearity, each moderator will be tested in a separate analysis. To determine whether the effect of changes in sleep efficiency on changes in CVD risk parameters vary by each of the aforementioned moderators, the analyses specified above for Hypothesis 2 will be modified to examine the main effect of a given moderator as well as the interaction effect of the moderator and sleep efficiency on each of the CVD risk variables.

D.4. Sample Size and Power Considerations

Calculations are based on Aims 1 and 2. Because each of the analyses will make use of repeated-measures data, statistical power will depend on the effective sample size (ESS). For Hypotheses 1, which will examine treatment effects associated with differences in sleep and cardiovascular outcomes, the ESS will be equivalent to the total number of observations (number of participants \times number of data collections) adjusted for intra-individual correlations. As the intra-individual, or intra-class, correlation (ICC) decreases, the ESS increases. Given that we anticipate substantial intra-individual variability on account of the intervention, an ICC of .50, representing an equal allotment of variance attributable to inter-individual differences and intra-individual variability, provides a conservative estimate of the ESS. With a sample of 150 contributing 3-time points of data each and an ICC of .50, the ESS would be 225. Even with 10% attrition post-intervention and then again at the 6-month follow-up, the ESS would be 215. Assuming equivalent attrition rates among the 100 CBT-I participants and 50 controls, this would have 80% power to detect treatment effects equivalent to Cohen's d of 0.41 via a two-tailed test with an alpha of .05. For reference, a meta-analysis on CBT-I (Okajima, Komada, & Inoue, 2011) found 12-month treatment effects on SOL, WASO, and sleep efficiency equivalent to $d = 0.45, 0.47$, and 0.54 , respectively. *Six-month follow-up CBT-I treatment effects in Talbot et al.'s (2014) RCT of CBT-I in persons with PTSD far exceeded these for SE ($d = 1.48$), SOL ($d = 1.31$), and TST ($d = 0.76$).* Moreover, Talbot et al. (2014) recorded large effects of CBT-I on 6-month increases in psychosocial functioning ($d = 1.02$). Although the specific impact of CBT-I on CVD risk remains untested, comparable behavioral-health interventions, such as stress management, have shown robust effects. For instance, in one study, 16 weeks of weekly 1.5-hour stress-management training compared to usual care was sufficient to achieve large increases in FMD ($d = 2.32$; Blumenthal,

[name] et al., 2005). In another study, a similar regimen of weekly group stress-management sessions was associated with significantly reduced time to adverse cardiac events, $HR = 0.26$ (95% CI: 0.07-0.90), in comparison to usual care. Given these effect sizes, the present study should have adequate power to detect treatment effects similar to those found in previous trials.

The second aim, which will examine within-person associations of changes in sleep efficiency with concomitant changes in cardiovascular indices, will have an ESS that is roughly equivalent to the total number of observations. With 150 participants contributing up to 2 change scores each, even with 10% attrition at each time point, the ESS is projected to be 256, which would have 80% power to detect an association equivalent to $\beta = .15$. A number of studies have established cross-sectional associations of sleep disturbance with cardiovascular risk factors (Spiegelhalder, Scholtes, & Riemann, 2010). In our own research, we have found that self-reported sleep disturbance is modestly associated with reduced heart-rate variability ($\beta = -.18$) and dyslipidemia (equivalent $\beta = .11$). We anticipate that these associations will be stronger in the proposed within-subjects analysis given the absence of random effects from between-person differences. Thus, the current trial should be sufficiently powered to detect even modest associations between concurrent changes in sleep efficiency and CVD risk parameters.

D.5. Data Sharing with Key Personnel Outside Duke

[name], at University of North Carolina at Chapel Hill, will perform some of the above-described statistical analyses in accordance with a sub-award to him. De-identified data will be shared with [name] via Box@Duke. No PHI, including dates, will be shared with [name].

E. STUDY TIMELINE

The overall data collection and analysis timeline is outlined in Table 3. Recruitment will occur in years 1 through 5. Intervention delivery and follow-ups will occur in years 1-5.

Table 3. Project Timeline

ACTIVITY	Year 1	Year 2	Year 3	Year 4	Year 5	Totals
Hiring/Training/Development	X					
Screening	26	48	47	47	31	199
Recruitment	20	35	35	35	25	150
DATA COLLECTION						
CVD & Sleep Measures	20	35	35	35	25	150
Treatment Waitlist	20	35	35	35	25	150
Post Assessment	15	38	34	32	23	142
6-month Assessment	0	40	38	41	23	142
Data Processing				X	X	
Data Analysis					X	

References

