Supplemental Aim: Explore the heterogeneity of CBT-I treatment response on sleep and CVD risk. We will explore moderators of improvements in sleep and CVD risk biomarkers following CBT-I including primary trauma type, insomnia disorder phenotype (objectively measured short sleep duration vs. objective normal sleep duration), medication use, biological sex, and minority status.

With respect to *expected outcomes*, the proposed work should establish whether unconsolidated sleep contributes to mechanisms conveying CVD risk burden in persons with PTSD. Identification of modifiable determinants of the relationship between PTSD and CVD risk is expected to have an important *positive impact* on the medical management of PTSD.

A. RESEARCH STRATEGY: SIGNIFICANCE AND INNOVATION

Several studies have now linked PTSD to increased cardiovascular disease (CVD) morbidity and

mortality (Boscarino, 2006; Edmondson et al., 2013; Flood et al., 2010), including a two-fold increase in the risk of premature death from CVD (Boscarino, 2008). While the distinct mechanisms underlying this association remain unclear, evidence suggests that PTSD contributes to CVD morbidity and mortality independent of health risk behaviors (e.g., smoking) and comorbid depression (Boscarino, 2008; Vaccarino et al., 2013). A recent review of the available evidence described PTSD as “a fast-track to premature cardiovascular disease” concluding that there was a lack of mechanistic evidence regarding the progression of atherosclerosis in PTSD, and a need to examine CVD risk biomarkers (Wentworth et al., 2013). Establishing the mechanism(s) linking PTSD to CVD is an essential next step in identifying therapeutic targets to reduce cardiovascular risk in this vulnerable population (Committee on Veterans’ Affairs House of Representatives Subject, 2010).

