Sleep duration will be defined as TST (calculated by subtracting all periods of wakefulness from the time spent in bed). WASO is calculated by summing wakefulness periods after initial sleep onset and before final awakening. Sleep efficiency is defined as the ratio of total sleep time divided by TIB (TST/TIB). Sleep fragmentation (a secondary outcome) is defined as the sum of percent mobile and percent immobile bouts less than 1-minute duration to the number of immobile bouts for a given interval (Respironics Incorporated, 2008). Actigraphy will be used as the primary source for these variables (Lauderdale, Knutson, Yan, Liu, & Rathouz, 2008). Scoring of actigraphy data will proceed in accordance with the guidelines by the Society of Behavioral Sleep Medicine (Ancoli-Israel et al., 2015). The sleep diary will include queries about removal of the actigraphy watch from the wrist, and unusual activities during the monitoring period (e.g., travel), and these factors will be considered when scoring. The event marker will be used as the primary method for establishing “into bed” and “out of bed” times. However, when study participants fail to press the event marker, (i.e., no marker on actigraphy output), light sensor data and sleep diaries will be combined with accelerometry data to establish “into and out of bed” times.

C.5.2.4. Daily Sleep Diaries. Subjective sleep estimates will be obtained concurrent with actigraphy, using a Qualtrics survey. Participants will record their sleep using the recently developed consensus sleep diary (Carney et al., 2012) to assure comparability across insomnia research studies. Sleep diaries will be used to calculate averages for: TIB, sleep onset latency (SOL) (Marino et al., 2013), TST, WASO, and SE. The sleep diary is considered the gold standard of self-reported sleep (Buysse et al., 2006). We will use Duke Qualtrics to gather the daily sleep diaries.

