The study is designed as a two-arm trial to examine the effects of CBT-I on objective sleep parameters and CVD risk biomarkers. Statistical analyses will be performed using SAS, version 9.4 (SAS Institute, Cary, NC) and Mplus, version 7 (Muthén & Muthén, 2012). The first step in the analysis will be to calculate descriptive statistics, including graphical displays, to summarize all study variables. We will construct individual and mean trajectory plots of the longitudinal outcome variables to understand their general trends from baseline to post-intervention and 6-month follow-up. In addition, we will explore the variability and correlation structure of the longitudinal outcome variables. We will stratify by trauma exposure (combat or non-combat) and objectively measured sleep duration (<6 hours or \geq 6 hours).

Each of the study hypotheses will be examined using data collected at baseline, immediately following the 8-week intervention phase (i.e., post-intervention), and again at 6-month follow-up. Given nesting of these multiple observations within each participant, multilevel modeling (MLM) will be used to examine each set of hypotheses. MLM is a technique for analyzing repeated observations of data across multiple individuals (Searle, Casella, & McCulloch, 1992). Unlike repeated-measures ANOVA,

MLM uses all available data and can handle data missing at random. MLM can also accommodate imbalanced data and unequal variances.

To manage the problem of random positive findings when making multiple comparisons within each hypothesis (i.e., random significant findings occurring due to multiple proposed analyses), we will correct alpha using the “false discovery rate approach” described by Glickman (Glickman, Rao, & Schultz, 2014). This methodology differentiates random findings from hypothesis-driven outcomes and is more powerful than Bonferroni-type alpha adjustments that control the false-positive rate (Benjamini, 2010; Glickman, Rao, & Schultz, 2014; Schafer & Olsen, 1988; Searle, Casella, & McCulloch, 1992; Simes, 1986). Specifically, alpha correction will be applied to Aims 1 and 2 but not to the Supplemental Aim, given that any exploratory hypothesis that is supported would require validation with further research.

D.2. Missing Data Considerations

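### Objective sleep duration is planned as a moderator only in two categories; adding continuous baseline TST beside the phenotype contrast would recover information if moderation is gradual

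*Combined protocol and SAP*

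**What the plan says.** The Specific Aims list, among the moderators for the Supplemental Aim, "insomnia disorder phenotype (objectively measured short sleep duration vs. objective normal sleep duration". That wording fixes two categories but gives no hour value. D.3 carries the variable forward by name only, in its list of "potential moderators (trauma type, insomnia phenotype, medication use, biological sex, and minority status". The sleep outcomes are to be modelled as a function of "treatment, time, a given moderator, and their second- and third-order interactions", with one moderator per analysis. D.3 then modifies the Hypothesis 2 change-score models to add each moderator and its interaction with sleep efficiency. It does not say how the phenotype is coded, where it is cut, or which assessment defines it.

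The only cut-point is in D.1, among the descriptive statistics and trajectory plots, where the plan is to stratify by combat or other trauma and by "objectively measured sleep duration (<6 hours or" at least 6 hours. This is not a randomisation stratum, since C.3 stratifies randomisation by gender and smoking only.

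The underlying measure is continuous. C.5.2.3 states that "Sleep duration will be defined as TST (calculated by subtracting all periods of wakefulness from the time spent in bed", and actigraphy runs for one week at baseline, after treatment and at 6 months. D.1 treats the aim as exploratory: "alpha correction will be applied to Aims 1 and 2 but not to the Supplemental Aim". The power section, D.4, covers Aims 1 and 2 only.

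**The concern.** Splitting a continuous moderator treats everyone within a category as alike. If the benefit of CBT-I, or the link between change in sleep efficiency and change in CVD risk, varies gradually with baseline sleep duration, a two-group comparison tests that gradient less efficiently than TST itself would.

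The aim exists to find heterogeneity worth validating later, so its main failure would be to miss a moderator that is there. The interaction test starts weak: 150 people randomised 2:1, then divided again. If 30% slept under 6 hours (assumed), the short-sleep control group would be about 50 x 0.30 = 15 people.

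**Working it through.** **1. The plan's own figures (D.4).** Inputs: 150 participants, 3 time points, ICC 0.50, 10% attrition at each of two steps, 100:50 allocation, two-sided alpha 0.05, 80% power, d = 0.41.

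- A participant with m observations contributes m/(1 + (m-1) x 0.50). Complete data give 150 x 3/2 = 225.
- With attrition, 15, 13.5 and 121.5 participants contribute 1, 2 and 3 observations: 15 x 1 + 13.5 x 1.333 + 121.5 x 1.5 = 215.25.
- Detectable d = (1.960 + 0.842) x sqrt(1/71.67 + 1/143.33) = 0.405 (0.407 with t quantiles), which rounds to the stated 0.41.

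The plan's figures reproduce. It gives none for the moderator test.

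**2. Strength of the two-category test on the same effective sample size of 215.** Let p be the share under the cut (assumed; the document does not give it). The variance of the difference in d between subgroups is (1/71.67 + 1/143.33) x (1/p + 1/(1-p)).

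| p | Difference in d needed for 80% power | Power for a difference of 0.41 |
|---|---|---|
| 0.50 | 0.81 | 29% |
| 0.30 | 0.88 | 25% |
| 0.20 | 1.01 | 20% |

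**3. Information kept by the split, if TST is normal and moderation linear (both assumed).** This is the squared correlation between TST and its two-level version, phi(z_p)^2 / [p(1-p)], where phi is the standard normal density at the cut.

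| p | Kept | Lost | 150 people act like | Power if continuous TST has 80% |
|---|---|---|---|---|
| 0.50 | 0.637 | 36% | about 95 | 61% |
| 0.30 | 0.576 | 42% | about 86 | 57% |
| 0.20 | 0.490 | 51% | about 73 | 50% |

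The equivalent numbers are before attrition. The last column is Phi(2.802 x sqrt(kept) - 1.960). A simulation with N = 150 and 2:1 allocation gave 80% against 61% at p = 0.50, and 80% against 54% at p = 0.30.

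**4. Other assumptions.**

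- Uniform TST with linear moderation: the split keeps 3p(1-p), which is 0.75 at the median (25% lost), 0.63 at 30/70 and 0.48 at 20/80. A clearly bimodal distribution gives almost the same result at the median (0.748).
- Heavier-tailed or skewed TST with linear moderation: the split keeps less than under normality. At the median it kept 0.54 for a t distribution with 5 degrees of freedom, 0.50 for Laplace and 0.59 for a gamma with shape 4.
- A true step at 6 hours: the split loses nothing and the linear term is the weaker test. Where the split has 80% power, linear TST has 61%, 57% or 50% at p = 0.50, 0.30 or 0.20 (normal TST).

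**5. What recovery would buy.** At p = 0.50, a subgroup difference of 0.41 gives the split a standardised effect of 0.41/0.289 = 1.417. If moderation is linear and TST normal, continuous TST has 1.417/sqrt(0.637) = 1.776, and power Phi(1.776 - 1.960), about 43% rather than 29%.

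**The case against.** The best defence is that the two categories are the question. The Specific Aims pre-specify a phenotype contrast, and if short sleepers differ in kind, a two-group comparison is the right test and a linear term the worse one. That stands, and it is why the phenotype contrast should be neither replaced nor demoted.

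The second defence is consequence. The aim is exploratory, carries no alpha correction, and any positive finding is to be validated in further research. Recovering all of the assumed loss still leaves an underpowered interaction test. This also stands, and it limits the point to a low-cost improvement.

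Three stronger readings are tempting, and the document supports none of them.

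- A reader might take the 6-hour cut as the stated definition of the moderator. It is a reasonable inference, since no other cut for objective sleep duration appears, but D.3 does not state it.
- A reader might conclude that more than a third of the information is certainly lost. That needs roughly normal TST and linear moderation; the document reports neither, nor the share under 6 hours.
- A reader might suppose that people near 6 hours are sorted largely by night-to-night variation. No night-to-night figure is given, a week of recording reduces such noise, and measurement error would also weaken a continuous moderator.

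**Conclusion.** The point holds as a minor improvement. The Supplemental Aim plans objective sleep duration only as short versus normal, although a continuous one-week measure is collected, and no analysis uses that measure as a continuous moderator.

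The size is conditional: 36% to 51% of the information for cuts between 50/50 and 20/80 under normality and linearity, about 25% for uniform TST at the median, and nil for a true step at 6 hours. Because the document does not settle which case applies, having both analyses is better than either alone. Nothing here touches Aims 1 and 2 or the sample size.

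**What to change.** In D.3, keep the phenotype contrast and state the cut and the assessment that define it. Beside it, add baseline actigraphic TST as a continuous moderator in both parts of the aim:

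- treatment x time x TST, with lower-order terms, in the sleep-outcome models;
- TST and TST x change in sleep efficiency in the modified Hypothesis 2 models, where a treatment x time term would not fit.

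Check linearity with a spline or quadratic term. The 6-hour contrast cannot do this, because a gradient and a step both produce a difference between the two groups. The check matters particularly for sleep efficiency, a bounded ratio with TST as its numerator. Report model-estimated effects at several durations, for example 5, 6 and 7 hours.

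The cost is a sentence or two in D.3, with no new data, visits or participant burden. The downside is one more exploratory analysis and an assumed functional form.

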We will test our central hypothesis in a randomized controlled trial (RCT) designed to determine if reduced insomnia symptoms result in improved CVD risk among those with co-morbid PTSD and Insomnia Disorder (ID). Specific and established CVD morbidity and mortality biomarkers of risk will be examined, including vascular endothelial function measured by brachial artery flow-mediated dilation (FMD), nighttime blood pressure (BP) dipping measured using 24-hour ambulatory blood pressure monitoring (ABPM), arterial stiffness measured by central pulse wave velocity (PWV), and atherosclerotic cardiovascular disease (ASCVD) risk score (Bonnet & Arand, 2007; Bonnet & Arand, 2010; Routledge & McFetridge-Durdle, 2007; Tsuji et al., 1996; Verdecchia, Angeli, Gentile, Mazzotta, & Reboldi, 2011). Insomnia will be measured *via* a multi-modal assessment strategy, including self-report and actigraphy. The *rationale* for the proposed research is if it is established that insomnia-related sleep impairment is a modifiable CVD risk factor among those with PTSD, new innovative approaches to integrating sleep treatment with PTSD focused interventions can be developed and implemented.

We will randomize 150 individuals with co-morbid PTSD and ID to either an 8-week CBT-I intervention or to a minimal contact control condition. Insomnia severity and objective sleep parameters, quality of life measures, and biomarkers of CVD risk will be assessed at baseline, post-intervention, and at a 6-month follow-up. Specific Aims include:

AIM 1: Determine whether CBT-I improves (a) CVD risk biomarkers, (b) 10-year ASCVD risk, and (c) quality of life (QoL) in persons with PTSD. *Hypothesis 1:* Compared to the control condition, CBT-I will be associated with increased sleep-efficiency and decreased insomnia severity (manipulation check), improved CVD risk biomarkers (Hypothesis 1a) including (i) lower nighttime BP and enhanced nighttime BP dipping, (ii) augmented vascular endothelial function (FMD), (iii) reduced sympathetic nervous system (SNS) activity (catecholamines), lower 10-year ASCVD risk score (Hypothesis 1b) and improved quality of life (Hypothesis 1c).

AIM 2: Determine whether within-person changes in sleep efficiency are accompanied by improved CVD risk biomarkers and 10-year ASCVD risk. *Hypothesis 2:* Within-person improvements in sleep efficiency (N=150) will be associated with improvements in CVD risk biomarkers and reduced ASCVD risk score.

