In an innovative use of an established and well validated intervention for insomnia, we propose to examine the direct effects of sleep on biomarkers of CVD risk outcomes among persons with PTSD and comorbid insomnia disorder (ID; see Figure 1). In this 2-arm RCT, 150 participants with PTSD and ID will be randomized at a 2:1 ratio to either CBT-I, or a minimal contact control condition (CCC). We anticipate that we may need to consent and screen as many as 500 participants to reach this goal. Sleep efficiency as measured by actigraphy will be the primary sleep outcome measure. Other parameters [total sleep time (TST) wake after sleep onset (WASO), sleep fragmentation] will be measured with a multi-modal assessment strategy including validated self-report measures, sleep diaries collected *via* Qualtrics, and objective sleep measurement (i.e., actigraphy). Sleep diaries and actigraphy will be continuously collected for 10-weeks (including a week-long baseline, 8-week period for CBT-I or CCC, and one-week post treatment) and for a week-long period at the 6-month follow-up. The primary outcomes for this clinical trial are established biomarkers of CVD risk, including flow mediated dilation, SNS activity, nighttime BP, nighttime BP dipping, and ASCVD risk. These biomarkers will be assessed at three time points: baseline, post-intervention (8-weeks), and 6-month follow-up. The 6-month follow-up period will allow us to evaluate whether the intervention effects on CVD risk are sustained beyond the immediate post-intervention period. Timing for the 6-month follow-up visit will be 6 months after

the baseline assessment or three months after the post-intervention assessment, whichever is later. Participants in both arms will continue with usual medical care.

C.2. Recruitment

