C.6.1. Assessment of 24-hour Ambulatory Blood Pressure (ABP). We have experience measuring 24-hour ABP and will use the Oscar 2 ABP monitor (Suntech Medical Inc., Raleigh, NC), which has been validated by previous investigators (Goodwin, Bilous, Winship, Finn, & Jones, 2007; Jones, Bilous, Winship, Finn, & Goodwin, 2004). Clinic BP will be determined according to the new ACC/AHA guidelines (Whelton et al., 2018) with three readings taken after five minutes of quiet rest in a seated posture, each separated by 2 minutes, using the Oscar 2 BP monitor together with appropriate cuff size, and averaged to represent clinic BP. Subsequently, the ABP monitor will be programmed to take BP measurements every 20 minutes throughout the waking hours and every 30 minutes during the nighttime sleep period. We have used this procedure with excellent participant acceptability and compliance in numerous previous studies (Blumenthal, [name], & Gullette, 2000; Carels, [name], Szczepanski, & Blumenthal, 2000; Prather, Blumenthal, Hinderliter, & [name], 2011; [name] et al., 2011; [name], Thurston, Steffen, Blumenthal, Waugh, & Hinderliter, 2001). A successful 24-hour study will require at least 80% of the total readings to be valid, with no more than two consecutive hours lacking a valid reading (White et al., 2006). Unsuccessful ABP studies will be repeated.

In addition to mean 24-hour ABP, mean waking and nighttime ABP will be computed, with the nighttime sleep period defined by self-report and confirmed by actigraphy ([name] et al., 2001; [name] et al., 2011; [name] et al., 2002). Nighttime BP dipping will be defined as the percentage of the decline in nighttime systolic blood pressure (SBP) [(mean daytime SBP- mean nighttime SBP/mean daytime SBP) \times 100]; SBP dipping defined in this way is a continuous variable that will be a primary outcome measure in this proposed RCT. In addition, for descriptive purposes, a SBP dip \geq 10% will be classified as normal “dipper”, while $<10\%$ will be classified as “non-dipper”, with secondary analyses evaluating intervention effects on dipping status. Twenty-four-hour ABP assessments will be obtained at pre-randomization baseline, upon completion of the 8-week intervention, and at 6-month follow-up, in order to evaluate intervention effects on ABP and nighttime BP dipping.

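### D.3 announces six CVD risk variables but names five, and nighttime BP, a stated primary outcome, has no named analysis

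*Combined protocol and SAP*

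**What the plan says.** - **Primary outcomes (C.1).** The biomarkers named as primary are "flow mediated dilation, SNS activity, nighttime BP, nighttime BP dipping, and ASCVD risk". Nighttime BP and dipping are two entries.
- **Hypothesis 1a (Specific Aims, Aim 1).** The first item is "i) lower nighttime BP and enhanced nighttime BP dipping", again two effects.
- **Derivation (C.6.1).** Besides the 24-hour mean, "mean waking and nighttime ABP will be computed". Dipping is the percentage fall from mean daytime to mean nighttime SBP, and "SBP dipping defined in this way is a continuous variable that will be a primary outcome measure in this proposed RCT".
- **Analysis for Hypothesis 1a (D.3).** A model with treatment, time and their interaction is to be fitted to "each of the 6 CVD risk variables (24-hr SBP, nighttime SBP dipping, FMD, 24-hr epinephrine, and norepinephrine".
- **Analysis for Hypothesis 2 (D.3).** The change-score model is applied to the "change scores corresponding to the 6 aforementioned CVD risk variables", and part of the moderator analysis is built on that model.
- **Multiplicity (D.1).** A false discovery rate correction covers Aims 1 and 2, to deal with "making multiple comparisons within each hypothesis".
- **A further biomarker (Specific Aims).** The opening text also lists "arterial stiffness measured by central pulse wave velocity (PWV", which has no procedure in C.6 and no row in the measures table.

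**The concern.** The count in D.3 does not match its list, and the list does not match the trial's own statement of its primary outcomes. A miscount alone would be trivial. Here the printed list omits an outcome declared primary and placed first in Hypothesis 1a, and it includes 24-hr SBP, which neither place mentions. An analyst who follows the list would not test nighttime BP. An analyst who follows the count would have to choose the sixth variable without guidance. Either way, whether the nighttime result is tested would be settled outside the plan, possibly with data in hand.

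The measure matters to the trial's own argument: B.6.1 ranks nighttime BP above clinic and daytime ambulatory BP as a predictor of cardiovascular risk.

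**Working it through.** **1. The stated count.** The names in D.3 are 24-hr SBP, nighttime SBP dipping, FMD, epinephrine and norepinephrine, which makes 5. Taking the two catecholamines as one item gives 4. No reading of the printed list gives the stated 6.

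**2. Outcomes against analyses.**

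| Outcome | Named primary in C.1 | Listed in Hypothesis 1a | Named model in D.3 |
|---|---|---|---|
| FMD | yes | yes | yes |
| SNS activity (two catecholamines) | yes | yes | yes |
| Nighttime BP | yes | yes, first | **no** |
| Nighttime BP dipping | yes | yes | yes |
| ASCVD risk | yes | no (Hypothesis 1b) | yes, logistic |
| 24-hr SBP | **no** | **no** | yes |
| PWV | no | no | no |

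Nighttime BP is the only primary outcome named in C.1 without a named model.

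**3. What the sixth might be.** Adding nighttime SBP gives 5 + 1 = 6. So would adding PWV, or the count may be left over from some other measure. The text does not settle it.

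**4. Whether the listed BP variables cover the gap.** C.6.1 defines dip = (day - night)/day x 100. The documents give no SBP values, so I assume day/night pairs of 120/108, 130/117 and 140/126 mm Hg, each a 10.0% dip.

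- *Proportional fall of 3-5% in day and night.* The ratio night/day is unchanged, so the dip stays at 10.0%. Nighttime SBP falls by between 108 x .03 = 3.2 and 126 x .05 = 6.3 mm Hg.
- *Daytime rise of 4 mm Hg only.* 124/108 gives 12.9%, 134/117 gives 12.7%, 144/126 gives 12.5%. The dip rises by 2.5 to 2.9 points with no change at night, and looks like benefit.
- *Nighttime fall of 4 mm Hg only.* 120/104 gives 13.3%, 130/113 gives 13.1%, 140/122 gives 12.9%. The dip rises by 2.9 to 3.3 points, so dipping does detect this case.

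24-hr SBP would move in the first case, but it averages day and night and does not isolate the night.

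**5. Multiplicity.** Assume Benjamini-Hochberg at .05 with the Hypothesis 1a biomarkers as the family. The smallest step-up threshold is .05/5 = .010 for five outcomes and .05/6 = .0083 for six. If both follow-up visits count, it is .05/10 = .005 against .05/12 = .0042. The largest step is .05 in every case.

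**6. Power.** The D.4 figure is per test at unadjusted alpha .05. With 10% attrition at each follow-up, the effective sample size is 121.5 x 3/2 + 13.5 x 2/1.5 + 15 = 215.25 (stated 215). Taking 215 with 2:1 allocation, power at d = 0.41 is about 0.81 (stated 80%). Naming a sixth outcome does not alter it.

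**The case against.** The best reply is that the plan supplies everything except the name. D.1 says every hypothesis will be examined by multilevel models at all three visits; Hypothesis 1a contains nighttime BP; C.6.1 derives it and says the ambulatory recordings serve to assess intervention effects on ABP; and D.3 uses one model form throughout Hypothesis 1a. On this reading an item fell out of the list, and the count of 6 shows it. This is the simplest explanation, but the text does not establish it, and general statements of purpose do not name a nighttime analysis.

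Second, with fixed day and night weights, 24-hr SBP and dipping together determine nighttime SBP: night = S(1 - d)/(w_day + w_night(1 - d)), where S is 24-hr SBP and d the dip as a fraction. So no change in nighttime SBP can leave both unchanged. That is correct, and the information is not lost. Two separate tests of other quantities still do not amount to a test of the nighttime level.

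Four smaller points stand:

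- The multiplicity effect is slight. The family may also be the whole of Hypothesis 1, which includes the manipulation check, 1b and 1c; the thresholds above would then differ.
- C.1 and Hypothesis 1a say BP without specifying systolic.
- Both introduce their items as inclusive lists, so 24-hr SBP is not excluded; its status is simply unstated.
- PWV is a separate inconsistency and matters here only as a rival for the sixth place.

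**Conclusion.** The concern holds and should be fixed. Five variables are named against six stated, and the omission falls on an outcome that C.1 declares primary and Hypothesis 1a lists first. The same undefined list is carried into Hypothesis 2 and the false discovery rate correction. This is a contradiction within the plan that changes what is tested, so it goes beyond missing detail.

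The count and the cross-check of sections need no assumption. The dipping illustration rests on assumed SBP values. The thresholds rest on Benjamini-Hochberg and on the family taken. That the sixth variable was meant to be nighttime SBP is likely but unproven, and the conclusion does not depend on it.

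**What to change.** 1. Name mean nighttime SBP in the D.3 list. It is already derived under C.6.1, matches the systolic form of the other two BP variables, and brings the list to the stated six if 24-hr SBP is kept. If the sponsor meant a different sixth variable, nighttime SBP still has to be added and the count changed.
2. State whether 24-hr SBP is confirmatory or secondary.
3. Print one closed list with a matching count, and use it for Hypothesis 1a, for Hypothesis 2 and to define the false discovery rate family.
4. Reconcile PWV in the Specific Aims with that list.

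The cost is a dated wording change, made before outcomes are compared by arm. No new data are needed. Against the printed five, the smallest threshold goes from .010 to .0083 under the assumptions above; against the stated six, nothing changes.
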